### 3.3 Translational Objectives

(1) **Objective:** To demonstrate, within the limitations of a nonrandomized study, that sequential pembrolizumab and radiotherapy for locally advanced NSCLC with PD-L1

expression  $\geq 50\%$  increases the rate of circulating tumor DNA clearance compared to standard concurrent chemoradiotherapy.

- (2) **Objective:** To correlate PD-L1 TPS score and expression of alternative immune checkpoint molecules (e.g.: HHLA2, B7x, and B7-H3) with clinical outcomes.
- (3) **Objective:** To correlate baseline tumor mutational burden with clinical outcomes.
- (4) **Objective:** To correlate markers of immune activation and expansion of immune cell subsets with clinical outcomes.

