## 4.6.2 Rationale for Endpoints

### 4.6.2.1 Efficacy Endpoints

- Progression-free survival duration following study enrollment (primary endpoint).
  - Progression-free survival is a standard assessment of clinical benefit of treatments for locally advanced NSCLC.
- Duration of freedom from distant metastasis following study enrollment.
  - Freedom from distant metastasis is a standard assessment for patients with locally advanced NSCLC, who are at high risk of developing metastatic disease.
- Duration of freedom from intrathoracic disease progression following study enrollment.

- Freedom from intrathoracic disease progression is a standard assessment for patients with locally advanced NSCLC, who are at high risk of developing local/regional disease progression.
- Survival duration following study enrollment.
  - Overall survival is a standard assessment of clinical benefit of treatments for NSCLC.
- Disease progression during induction pembrolizumab for patients with PD-L1 expression  $\geq 50\%$ .
  - As induction pembrolizumab prior to radiotherapy for locally advanced NSCLC is a novel treatment approach, it will be important to characterize the rate of disease progression during induction therapy.

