#### **4.6.2.3 Translational Endpoints**

- Clearance of circulating tumor DNA following radiotherapy.

- Subjects in the PembroRT and ChemoRT cohorts will undergo circulating tumor DNA testing at study entry and several weeks after the completion of thoracic radiotherapy. Circulating tumor DNA clearance may be a powerful predictor of disease control following conventional treatment for locally advanced NSCLC[39]. We will test the prognostic utility of circulating tumor DNA testing for patients treated with pembrolizumab and radiotherapy and compare rates of circulating tumor DNA clearance in the two study cohorts.
- PD-L1 TPS score and expression of alternate immune checkpoint molecules.
  - Tumor PD-L1 expression as determined by immunohistochemistry (IHC) has been implicated as a predictive biomarker for benefit from treatment with PD-1/PD-L1 inhibitors[40, 41]. We will assess baseline PD-L1 expression for each study subject using our in-house and FDA-approved immunohistochemical assay on archival FFPE tumor tissue. Sections cut from FFPE blocks will be deparaffinized and subjected to heat-induced epitope retrieval. Slides will be incubated with the primary antibody (monoclonal mouse anti-PD-L1, clone 22C3) and visualized using the EnVision FLEX system on the Dako Autostainer Link 48. Protein expression will be quantified as tumor proportion score (TPS), which is the percentage of tumor cells demonstrating PD-L1 membrane staining. Subjects will be assigned to the PembroRT or ChemoRT cohort based on PD-L1 expression, using a cutoff of 50%. Within each cohort, we will explore if PD-L1 expression level is associated with clinical outcomes, including progression-free survival and overall survival.
  - We will also quantify baseline tumor expression of alternate immune checkpoint molecules in peripheral blood as well as from fresh tumor material (if available). From blood samples, peripheral blood mononuclear cells will be isolated using Ficoll Paque density gradient centrifugation, followed by antibody labeling and analysis. From biopsy specimens, tumor will be dissociated without enzymatic digestion, followed by antibody labeling for multi-color flow cytometric analysis that will focus on expression of HHLA2, PD-L1, PD-L2, B7-H3, and B7x (B7-H4/B7S1) in CD8-positive T cells and regulatory cells. We will explore if expression of immune checkpoint molecules is associated with clinical outcomes.
- Tumor mutational burden.

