  - Tumor mutational burden has been identified as a predictive factor for response to immune checkpoint blockade in several settings[42-44]. We will utilize a validated commercial platform to explore tumor mutational burden as a prognostic factor for study subjects.
- Markers of immune activation.
  - The PD-1 receptor and its ligands define a novel regulatory pathway with potential inhibitory effects on T, B, and monocyte responses[41, 45]. We will characterize how study therapy affects several markers of immune activation

throughout the treatment course. Blood collected from study subjects will be centrifuged to isolate peripheral blood mononuclear cells, and flow cytometry will be performed for immunophenotyping of mononuclear cells using several panels to quantify populations of B cells, CD4 and CD8 cells, natural killer cells, monocytes, and myeloid and plasmacytoid dendritic cells. CD4, CD8, and regulatory T cell populations will be tested for markers of activation, including expression of PD-1, ICOS, and CTLA-4. We may identify predictors of long-term clinical outcomes. Additionally, we may identify bottlenecks where treatment resistance may be overcome by the addition of additional immunomodulatory agents in the future.

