## 8.0 STATISTICAL ANALYSIS PLAN

### 8.1 Statistical Analysis Plan – Primary Endpoint and Sample Size Calculation

The **primary endpoint** is progression-free survival (PFS) in the PembroRT cohort one year following study enrollment. PFS duration will be defined as the time from study registration to the date of disease progression or death from any cause. In cases where a scan is concerning for progressive disease based on RECIST 1.1 criteria, and progression is confirmed on a subsequent scan 4-8 weeks later (satisfying iRECIST criteria for progression), the date of disease progression would be the date of the first scan demonstrating progression. PFS rates will be estimated using the Kaplan-Meier Survival method, from which the probability of PFS at various time points and corresponding 95% confidence intervals will be estimated. If a patient is lost to follow-up without having disease progression, progression-free survival will be censored at the date of the patient's last clinic visit. Based on published multi-institutional trials and data from our institution, we expect the one-year progression-free survival rate ( $H_0$ ) to be to 40% with standard chemoradiotherapy. We hypothesize that this rate will be at least 65% ( $H_1$ ) for subjects in the PembroRT cohort. A one sample two-sided log-rank test will be used to compare the one-year PFS rate in the PembroRT cohort against the expected rate with ChemoRT. We plan to accrue **25 subjects to the PembroRT cohort**. Assuming that the accrual period will last 18 months and that event rates will follow an exponential distribution, this sample size will provide 81% power to detect an improvement in PFS at 1 year at a 5% level of significance using a one sample two-sided log-rank test [48, 49].

The ChemoRT cohort will be open to accrual while accrual to the PembroRT cohort is ongoing. We expect that approximately 40% of patients with locally advanced NSCLC have PD-L1 expression of at least 50%. We therefore expect that approximately 38 subjects will be enrolled and treated with standard concurrent chemoradiotherapy as part of this trial, which will yield a **total sample size of approximately 63 subjects**.

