### 8.2 Statistical Analysis Plan – Secondary Endpoints

Time-to-event outcomes (overall survival, freedom from distant metastasis, freedom from intrathoracic progression, freedom from hospitalization) will be analyzed using the Kaplan-Meier method, from which rates at various time points and corresponding 95% confidence intervals will be estimated. Exploratory comparisons for time-to-event outcomes between the PembroRT and ChemoRT cohorts will be performed using log-rank tests. Univariate and

multivariable Cox regression models will be used to evaluate associations between time-to-event outcomes and clinical covariates, including study cohort.

Rates of radiographic responses and disease progression during induction pembrolizumab for subjects in the PembroRT cohort will be described using counts and percentages. Logistic regression models will be used to evaluate potential predictors of response or progression (e.g.: PD-L1 TPS).

Hospitalization rates and adverse event rates, scored using CTCAE as well as PRO-CTCAE, will be presented as counts and percentages. Exploratory comparisons between the PembroRT cohort and the ChemoRT cohort will be performed using chi-square or Fisher Exact testing, as appropriate.

Daily step counts throughout the study period will be presented using descriptive statistics and will be analyzed using a generalized linear mixed-model for repeated measures.

Rates of circulating tumor DNA clearance will be presented as counts and percentages, and predictors of circulating tumor DNA clearance will be explored using chi-square or Fisher exact testing, as appropriate. Exploratory analyses will be performed to evaluate PD-L1 expression, expression of alternative immune checkpoint molecules (e.g., HHLA2, B7x, and B7-H3), baseline tumor mutational burden, and markers of immune activation (e.g., expansion of T4/T8 subsets, myeloid derived suppressor cell levels, expansion of T-cell repertoire) as predictors of PFS and overall survival.

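### Post-baseline markers are to predict PFS and OS counted from registration, with no landmark or time-dependent method stated

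*Combined protocol and SAP*

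**What the plan says.** Section 8.2 lists the candidate predictors of PFS and overall survival. PD-L1 and tumor mutational burden are baseline measurements. The immune-activation group is described as "expansion of T4/T8 subsets, myeloid derived suppressor cell levels, expansion of T-cell repertoire) as predictors of PFS and overall survival", and expansion needs a second sample. Translational objective 3.3(4) is "To correlate markers of immune activation and expansion of immune cell subsets with clinical outcomes". Section 4.6.2.3 confirms repeated measurement: "We will characterize how study therapy affects several markers of immune activation", over the course of treatment.

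For ctDNA, Section 4.6.2.3 places testing "at study entry and several weeks after the completion of thoracic radiotherapy" and adds: "We will test the prognostic utility of circulating tumor DNA testing for patients treated with pembrolizumab and radiotherapy". The same section plans a comparison of clearance between the cohorts. Section 8.2 treats clearance as an outcome, with counts, percentages and predictors of its own. It gives no denominator and does not list clearance among the predictors of PFS and OS.

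The clock is fixed in Section 8.1: "PFS duration will be defined as the time from study registration to the date of disease progression or death from any cause". Section 4.6.2.1 counts overall survival from enrollment. Section 8.2 mentions no landmark, time-dependent covariate or delayed entry, and no rule for patients who lack the later sample.

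**The concern.** A patient can be classed as expanded or cleared only at the later sample. If follow-up is counted from registration, events before that sample can be credited to the wrong marker group. The plan leaves two routes open.

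- **Patients without a later sample.** Confirmed progressors stop treatment (Section 5.5) and move to telephone survival follow-up (Section 7.1.5.3), so some may never give the sample. If they are coded as marker-negative, the positive group is event-free up to the sample by construction.
- **Samples taken after the event.** Section 8.1 dates progression to the first progressive scan. Section 7.1.2.6 lets treatment continue while confirmation is awaited, 4 to 8 weeks later. A marker can therefore be read after the PFS event that it is meant to predict.

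Either route can make a marker with no prognostic value look protective. Section 4.6.2.3 hopes that this work will identify predictors of long-term outcome and point to further agents, so a false lead would have consequences.

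**Working it through.** **Inputs from the plan.** One-year PFS is 40% under the null and 65% under the alternative, with exponential event times, 18 months of accrual, 25 PembroRT and about 38 ChemoRT patients (Section 8.1). Induction is three cycles every three weeks, so 3 × 3 = 9 weeks (Sections 3.2(4) and 5.2.1.1).

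**Assumptions.** The serum-sampling row of the flow chart is not readable in the text available, so I take marker times of weeks 10, 14 and 18 for PembroRT and weeks 8 to 12 for ChemoRT, which has no induction phase. The marker has no true effect and is positive in half of the patients. Follow-up after the last entry is not stated.

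**Step 1: the plan's own figure.** The plan gives no figure for the marker analyses. Its power statement uses the same exponential model. Hazards are −ln 0.40 = 0.916 and −ln 0.65 = 0.431 per year, a ratio of 0.470. The one-sample log-rank statistic (O − E)/√E, two-sided 5%, n = 25, with an assumed 12 months after the last entry, gives 80.6% power against the stated 81%. The model is therefore consistent with the plan.

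**Step 2: events before the marker is known.** The share still event-free at week w is S(w) = p^(w/52), where p is one-year PFS.

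| One-year PFS | Week | S(w) | Events before sample, of 25 |
|---|---|---|---|
| 65% | 10 | 0.920 | 2.0 |
| 65% | 18 | 0.861 | 3.5 |
| 40% | 10 | 0.838 | 4.0 |
| 40% | 18 | 0.728 | 6.8 |

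**Step 3: simulated hazard ratios for a null marker, PFS from registration.**

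| Handling | 65% one-year PFS | 40% one-year PFS |
|---|---|---|
| Unsampled coded negative, weeks 10 / 14 / 18 | 0.73 / 0.68 / 0.61 | 0.70 / 0.60 / 0.52 |
| Only patients sampled while event-free | 0.98 / 1.02 / 1.01 | 1.03 / 1.01 / 0.97 |
| Landmark at the sample, event-free patients | 0.98 / 1.02 / 1.01 | 1.03 / 1.01 / 0.97 |

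With n = 25, 65% PFS and week 18, the false-positive rate is 9% when unsampled patients are coded negative and 4% with the landmark.

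**Step 4: samples taken after progression.** Suppose all patients are sampled, and progression lowers positivity from 50% to 25% (assumed). The false hazard ratio is 0.81 at week 14 and 0.77 at week 18. If positivity falls to 10%, it is 0.71 and 0.68. The landmark again returns 0.97 to 1.01.

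**Step 5: absolute rates among patients sampled while event-free.** One-year PFS from registration becomes p/S(w). At 65% it is 0.65/0.920 = 71% (week 10) to 0.65/0.861 = 75% (week 18). At 40% it is 0.40/0.838 = 48% to 0.40/0.728 = 55%. Simulation gives 70% to 75% and 47% to 55%, so the inflation is about 5 to 15 points.

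**Step 6: clearance by cohort.** Suppose 60% of all patients clear in each cohort (assumed), and every patient with an earlier PFS event goes unsampled. PembroRT at 65%, week 18: 0.60/0.861 = 70%. ChemoRT at 40%, weeks 8 to 12: S = 0.869 to 0.809, so 0.60/0.869 = 69% to 0.60/0.809 = 74%.

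**The case against.** The strongest reply is that Section 8.2 calls this work exploratory. No primary or secondary endpoint, sample size or decision rule depends on it, and a landmark can be chosen at analysis. This stands and sets the weight of the point. Even so, silence leaves sound and badly biased versions equally open once the data have been seen.

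The reply also has force on detail. No section says that unsampled patients will be coded negative for PFS or OS, so the hazard ratios of 0.52 to 0.73 describe what the plan permits, not what it states. ctDNA as a predictor rests on one general sentence in Section 4.6.2.3, which gives no endpoint, time origin or model. Immune markers are followed throughout treatment, so expansion could be read earlier. At week 6, only about 5% have had an event at 65% one-year PFS (S = 0.952, or 1.2 of 25), and the distortion is smaller.

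Three stronger readings are tempting, and the documents support none of them.

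- A reader might infer that the analysis is limited to sampled patients and that this creates the false association. The plan does not say so. Restricting it to patients sampled while event-free leaves the hazard ratio at about 1.0.
- A reader might infer that PembroRT clearance is inflated relative to ChemoRT, because only PembroRT has an induction phase. At the plan's own rates the losses before sampling are similar (14% against 13 to 19%), and step 6 shows no difference or the reverse. Section 5.5 also keeps patients in the study after treatment stops, and no text says that sampling ends.
- A reader might apply false-positive rates for all 63 patients to ctDNA. The prognostic sentence concerns patients given pembrolizumab and radiotherapy, a cohort of 25.

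**Conclusion.** The concern holds in a limited form. Post-baseline immune markers are planned as predictors of PFS and OS from registration or enrollment, ctDNA is to be tested for prognostic value, and no method deals with events that come before the marker is known. The size depends on a choice that the plan does not make. It ranges from no bias in the hazard ratio (with inflated absolute PFS) to a spurious halving of the hazard at the extreme of week 18, 40% one-year PFS and unsampled patients coded negative.

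These figures rest on assumed sampling weeks, a 50% positive marker and, for sampling after progression, an assumed fall in positivity. They were computed for PFS only. Baseline PD-L1 and tumor mutational burden are unaffected. The point is minor: a cheap improvement to exploratory analyses.

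**What to change.** Add to Section 8.2:

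- **Marker associations.** For every post-baseline marker, start PFS and OS at a landmark at the sampling visit and include only patients event-free then, or enter the marker as a time-dependent covariate. Name the visit for each marker.
- **ctDNA clearance.** Report the rate over all patients with detectable ctDNA at baseline, counting progression or death before the second sample as not cleared. Give the rate among sampled patients as a sensitivity analysis, with the number unsampled and the reasons, by cohort.
- **Keep the two apart.** Do not carry the not-cleared coding of early failures into the PFS or OS models, where it would create the bias shown in step 3.
- **ctDNA as a predictor.** If clearance is to be tested against PFS or OS, list it in Section 8.2 under the same landmark rule.

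The cost is a few sentences, with no new visits, samples or patients. The downside is that early events leave the landmark analysis: about 2.0 to 3.5 of 25 PembroRT patients at 65% one-year PFS, or 4.0 to 6.8 at 40%, for samples at weeks 10 to 18.

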## **9.0 LABELING, PACKAGING, STORAGE AND RETURN OF CLINICAL SUPPLIES**

### **9.1 Investigational Product**

The investigator shall take responsibility for and shall take all steps to maintain appropriate records and ensure appropriate supply, storage, handling, distribution and usage of investigational product in accordance with the protocol and any applicable laws and regulations.

Pembrolizumab will be provided by Merck as summarized in Table 8.

Table 8 Product Descriptions

Product Name & Potency	Dosage Form
Pembrolizumab 100 mg/ 4mL	Solution for Injection

### **9.2 Packaging and Labeling Information**

Supplies will be labeled in accordance with regulatory requirements.

### **9.3 Clinical Supplies Disclosure**

This trial is open-label; therefore, the participant, the trial site personnel, the Sponsor and/or designee are not blinded to treatment. Drug identity (name, strength) is included in the label text; random code/disclosure envelopes or lists are not provided.

### **9.4 Storage and Handling Requirements**

Clinical supplies must be stored in a secure, limited-access location under the storage conditions specified on the label.

Receipt and dispensing of trial medication must be recorded by an authorized person at the trial site.

Clinical supplies may not be used for any purpose other than that stated in the protocol.

### **9.5 Returns and Reconciliation**

The investigator is responsible for keeping accurate records of the clinical supplies received from Merck or designee, the amount dispensed to and returned by the participants and the amount remaining at the conclusion of the trial.

Upon completion or termination of the study, all unused and/or partially used investigational product will be destroyed at the site per institutional policy. It is the Investigator's responsibility to arrange for disposal of all empty containers, provided that procedures for proper disposal have been established according to applicable federal, state, local and institutional guidelines and procedures, and provided that appropriate records of disposal are kept.

## **10.0 ADMINISTRATIVE AND REGULATORY DETAILS**

## 11.0 APPENDICES

### Appendix 1: ECOG Performance Status

Grade	Description
0	Normal activity. Fully active, able to carry on all pre-disease performance without restriction.
1	Symptoms, but ambulatory. Restricted in physically strenuous activity, but ambulatory and able to carry out work of a light or sedentary nature (e.g., light housework, office work).
2	In bed <50% of the time. Ambulatory and capable of all self-care, but unable to carry out any work activities. Up and about more than 50% of waking hours.
3	In bed >50% of the time. Capable of only limited self-care, confined to bed or chair more than 50% of waking hours.
4	100% bedridden. Completely disabled. Cannot carry on any self-care. Totally confined to bed or chair.
5	Dead.

\* As published in Am. J. Clin. Oncol.: *Oken, M.M., Creech, R.H., Tormey, D.C., Horton, J., Davis, T.E., McFadden, E.T., Carbone, P.P.: Toxicity And Response Criteria Of The Eastern Cooperative Oncology Group. Am J Clin Oncol 5:649-655, 1982.* The Eastern Cooperative Oncology Group, Robert Comis M.D., Group Chair.

**Appendix 2: Common Terminology Criteria for Adverse Events V4.0 (CTCAE)**

The descriptions and grading scales found in the revised NCI Common Terminology Criteria for Adverse Events (CTCAE) version 4.0 will be utilized for adverse event reporting. (<http://ctep.cancer.gov/reporting/ctc.html>)

## Appendix 3: Contraceptive Guidance and Pregnancy Testing

### Woman of Childbearing Potential (WOCBP)

A woman is considered fertile following menarche and until becoming post-menopausal unless permanently sterile (see below)

Women in the following categories are not considered WOCBP:

- Premenarchal
- Premenopausal female with 1 of the following:
  - Documented hysterectomy
  - Documented bilateral salpingectomy
  - Documented bilateral oophorectomy

Note: Documentation can come from the site personnel's review of the participant's medical records, medical examination, or medical history interview.

- Postmenopausal female
  - A postmenopausal state is defined as no menses for 12 months without an alternative medical cause.
    - A high follicle stimulating hormone (FSH) level in the postmenopausal range may be used to confirm a postmenopausal state in women not using hormonal contraception or hormonal replacement therapy (HRT). However, in the absence of 12 months of amenorrhea, confirmation with two FSH measurements in the postmenopausal range is required.
  - Females on HRT and whose menopausal status is in doubt will be required to use one of the non-hormonal highly effective contraception methods if they wish to continue their HRT during the study. Otherwise, they must discontinue HRT to allow confirmation of postmenopausal status before study enrollment.

